### **12.2 Safety Monitoring and Mitigation Plan**

The liver function (total and direct bilirubin, alkaline phosphatase, ALT, AST, LDH, albumin, and total protein) of study subjects will be monitored closely throughout the study as indicated above in [Section 9.13](#).

Key potential anticipated risks are:

- Development of transaminitis due to cell-mediated immunity to the AAV capsid protein, the engineered ZFNs, or the hIDUA delivered by SB-318; to minimize the potential immune response and to preserve hepatic function, prednisone or equivalent corticosteroid will be administered prophylactically starting 2 days prior to the SB-318 infusion and will be tapered over a period of approximately 20 weeks (see [Appendix 3](#)).
- Reduction in albumin synthesis; this is not expected given the small fraction (<1%) of transduced cells in which the albumin locus will be disrupted (see [Section 1.7](#)), and has not been observed in animal studies in which levels of transduction and albumin locus disruption exceeded by several fold those expected in humans.
- Off-target modification at the SMCHD1 locus; this is not expected given that no off-target activity has been observed at clinically relevant levels of albumin on-target activity in human cells *in vitro* (see [Section 8.1.2](#)).

### **12.3 Safety Monitoring Committee**

An external SMC with appropriate medical and scientific expertise will have oversight of the study.

The SMC will be convened after the completion of each cohort to advise whether it is safe to proceed with the next dose cohort, and to provide recommendations on pediatric dosing and expansion of any cohort. The SMC may also be convened at any time if there are excessive or unexpected toxicities associated with the conduct of the protocol. Specifically, the SMC will be convened if the following occurs:

- Any one Grade 3 or higher AE, or any two Grade 2 AEs in the same system organ class that persist for more than 2 weeks with therapy, provided these AEs are not related to the primary MPS I disease or treatment of the MPS I disease.
- SAE not related to the primary MPS I disease
- Death of a subject.
- Development of a malignancy.

The SMC will then evaluate all data to advise whether the changes should be made to the study or whether accrual and dosing should be halted. In addition, no further dosing of subjects will be performed until a substantial amendment is submitted to the regulatory authority(ies) for review, and the amendment has been approved by the site IRB/IEC or equivalent.

The SMC may also recommend changes to the enrollment of cohorts based on cumulative adult and pediatric safety and efficacy data from this and similar ongoing first-in-human clinical trials that are sponsored by Sangamo and that use *in vivo* rAAV2/6-based gene transfer of ZFNs. Specifically, study SB-913-1602 in MPS II subjects uses identical ZFNs (SB-47171 and SB-47898) as the present study in combination with a different donor cDNA (encoding iduronate-2-sulfatase) (Clinicaltrials.gov NCT03041324). Given the similarities of the approaches, relevant data from study SB-913-1602 and other trials sponsored by Sangamo may be shared with the SMC to expand the clinical experience, particularly as it relates to safety and dose, and such data can be used by the SMC to inform its recommendations for the present study.

When no further enrolling or dosing decisions are required of the SMC, the SMC will no longer meet. Sangamo will continue to review subject safety data on an ongoing basis.

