Almost all patients with MPS IH undergo HSCT. If patients are diagnosed early (at <2.5 years), therapeutic intervention by HSCT can prevent or reverse most clinical features including the neurocognitive symptoms. Unfortunately, the mortality rate after HSCT has been reported to be 15%, and survival rate with successful engraftment is 56%, although recent improvements in HSCT procedure have improved overall outcomes ([Boelens et al. 2013](#)).

ERT has been shown to improve pulmonary function, hepatosplenomegaly, and exercise capacity, and to lead to improved health-related quality of life. ERT should be instituted as early as possible. However, drawbacks of ERT include the need for life-long treatment; development of neutralizing antibodies; inability to cross the blood brain barrier; continued cardiac, orthopedic, and ocular complications; and the inconvenience of weekly intravenous (IV) infusions. These drawbacks underscore the urgent need to develop a broader array of curative therapies for MPS I.

The objective and rationale for the proposed SB-318 investigational therapy is to abrogate or decrease the need for ERT using *in vivo* genome editing. The proposed treatment employs recombinant adeno-associated virus (rAAV) comprising engineered zinc finger nucleases (ZFNs) to site-specifically integrate a corrective copy of the human iduronidase enzyme (IDUA)

[figure not shown]
transgene into the genome of subjects' own hepatocytes *in vivo*. Integration of the hIDUA transgene is targeted to intron 1 of the albumin locus, resulting in stable, high level, liver-specific expression and secretion of hIDUA into the blood. Placement of the hIDUA transgene under the control of the highly expressed endogenous albumin locus is expected to provide permanent, liver-specific expression of hIDUA for the lifetime of an MPS I patient.

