#### **10.3 Recording of an Adverse Event**

The Principal Investigator is responsible for evaluating all AEs, obtaining supporting documents, and determining that documentation of the event is adequate. He/she is responsible for determining the severity of the AE and its relationship to the investigational drug. The Principal Investigator may delegate these duties to sub-investigators but must assure that these sub-investigators are qualified to perform these duties under the supervision of the Principal Investigator.

All AEs will be recorded in the subject's CRF. The detailed description of the event will include appropriately graded severity of the AE and its relationship to the investigational product. Severity will be categorized by toxicity grade according to the Common Terminology Criteria for Adverse Events (CTCAE) Version 4.03.

AEs not listed in the Common Terminology Criteria for Adverse Events version 4.03 will be evaluated by using the following criteria:

- Grade 1, Mild: Symptoms cause no or minimal interference with usual social and functional activities.
- Grade 2, Moderate: Symptoms cause greater than minimal interference with usual social and functional activities.

- Grade 3, Severe: Symptoms cause inability to perform usual social and functional activities.
- Grade 4, Potentially Life-threatening: Symptoms cause inability to perform basic self-care functions OR medical or operative intervention indicated to prevent permanent impairment, persistent disability, or death.
- Grade 5: Outcome of AE is death.

The relationship of the AE to the investigational drug will be determined by the Principal Investigator. Any AE that does not meet the definition of a suspected AR will be categorized as Not Related.

Any Grade 3 and 4 clinical laboratory results that represents an increase in severity from Baseline will be reported as an AE if it is not associated with a diagnosis already reported on the CRF. A Grade 1 or 2 clinical laboratory abnormality should be reported as an AE only if it is considered clinically significant by the Principal Investigator.

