#### 11.4 ERT Withdrawal

ERT is beneficial but has significant drawbacks, including the need for continuous life-long treatment, development of neutralizing antibodies, lack of efficacy in the brain (due to inability to cross the blood-brain barrier), continued cardiac, musculoskeletal, and upper airway complications, and the inconvenience and cost of weekly IV infusions (Tomanin et al, 2014).

The goal of SB-318 treatment is to abrogate or decrease the need for ERT by using engineered ZFNs to site-specifically integrate a corrective copy of a hIDUA transgene into the genome of the subject's own hepatocytes *in vivo*, resulting in life-long, liver-specific expression of hIDUA.

Subjects who have received SB-318 may no longer require weekly administration of ERT, and may be considered for withdrawal of ERT (if applicable).

ERT withdrawal will be a controlled process, with additional safety monitoring to reduce potential risks to the subject, and is an optional part of the study.

ERT withdrawal may be initiated by the Principal Investigator after consultation with the Sponsor, and only in subjects who are willing and who meet all of the following criteria:

- are  $\geq 12$  weeks post-administration of SB-318;
- are medically stable and can tolerate temporary discontinuation of ERT in the judgement of the Principal Investigator; and
- agree to additional safety monitoring and clinical laboratory tests until the ERT Withdrawal Follow-Up visit (see [Appendix 2](#)).

Study visits associated with ERT withdrawal may occur concurrent with or independent of regular scheduled study visits, but should be combined with regular scheduled study visits whenever possible to reduce study burden. When combined, assessments associated with ERT withdrawal that are duplicated at the regular scheduled study visits should be waived (see [Appendix 1](#)). The ERT Withdrawal Follow-Up visit can occur at any time up to 12 weeks after ERT withdrawal at the discretion of the Principal Investigator.

ERT does not need to be restarted after the ERT Withdrawal Follow-Up visit. However, ERT may be re-initiated at any time based on clinical circumstances or at the judgement of the Principal Investigator.

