9.3. Pregnancy Test

Urine pregnancy test will be conducted for females of childbearing potential at Screening and Baseline, at Day 0 if >7 days from Baseline. It will be performed until Week 48 or until 3 consecutive plasma samples are negative for AAV2/6, whichever happens first. If urine pregnancy test result is positive, equivocal or impractical, a serum pregnancy test will be performed to confirm. The data will be presented in a listing.

10. Safety Monitoring Committee

An independent SMC composed of appropriate medical and scientific expertise will provide oversight of the study. For the cohort safety review, the SMC will be convened after the completion of each cohort (at least four weeks after the last subject within that cohort has received the study drug) to determine if it is safe to escalate to the next dose cohort. For the rolling safety review, the SMC will meet to review all available safety data approximately every 4-6 months after the first Cohort Safety Review. These meetings may be combined with subsequent cohort safety review meetings as appropriate.

The SMC may be convened at any time if there are excessive or unexpected toxicities associated with the conduct of the protocol. Specifically, the SMC will be convened earlier if the following occurs:

- Any two Grade 2 AEs in the same SOC that last more than 2 weeks with treatment or any one Grade 3 or greater AE, if these AEs are not related to the primary MPS I disease or treatment of the MPS I disease.
- SAEs not related to the primary MPS I disease.
- Death of a subject.
- Development of a malignancy.

Data analyses for SMC review will be presented in a separate document.

When no further enrolling or dosing decisions are required of the SMC, the SMC will no longer meet. Sangamo will continue to review subject safety data on an ongoing basis.

11. Changes to the Statistical Analysis Section of the Protocol

Secondary endpoint, change of baseline over time of dose of Aldurazyme (or equivalent ERT), will no longer be summarized.

12. References

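### Serious worsening of MPS I during ERT withdrawal does not prompt an SMC meeting, because the event triggers exclude disease-related events

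*Protocol*

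**What the plan says.** Protocol 12.3 lists four events that require the SMC to be convened.

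- A Grade 3 or higher adverse event (AE), or two Grade 2 AEs in one system organ class lasting more than 2 weeks despite therapy, "provided these AEs are not related to the primary MPS I disease or treatment of the MPS I disease".
- Any "SAE not related to the primary MPS I disease".
- "Death of a subject".
- "Development of a malignancy".

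Section 11.5 and the synopsis rows on the SMC and on stopping rules carry the same bullets. SAP section 10 repeats them, including "SAEs not related to the primary MPS I disease". Section 11.2 applies the AE exclusion to the dosing pause but has no SAE trigger.

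Section 11.4 allows optional ERT withdrawal from 12 weeks after SB-318. It states that "ERT withdrawal will be a controlled process, with additional safety monitoring to reduce potential risks to the subject". The investigator starts the withdrawal after consulting the sponsor, and it may be repeated. Under 9.35 the investigator and the Medical Monitor judge whether ERT should resume. None of these sections gives the SMC a role.

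On the value of the therapy being stopped, section 1.1 says that "ERT has been shown to improve pulmonary function, hepatosplenomegaly, and exercise capacity".

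**The concern.** Excluding disease-related events is reasonable while background ERT is stable, because it keeps ordinary progression of MPS I from repeatedly convening the committee. Under 11.4, however, the study itself removes a therapy that the protocol describes as effective. Loss of lung function, organ enlargement or loss of exercise capacity is then the harm one would look for, and it falls naturally under the exclusion.

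Reducing the need for ERT is the stated goal of SB-318, so a failed withdrawal bears on both safety and that goal. Another subject's withdrawal, or a repeat in the same subject after the required 12 weeks back on ERT, could start before the SMC has looked at the first failure.

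**Working it through.** The question is mainly textual; the only arithmetic is on timing. The plan gives no figure to reproduce.

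**Triggers set against the event.** Take a Grade 3 respiratory decline, or a hospitalization, with onset off ERT and attributed to MPS I.

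| Trigger in 12.3 | Disease exclusion? | Convenes the SMC? |
|---|---|---|
| Grade 3+, or two persistent Grade 2 | Yes: disease or its treatment | No |
| SAE | Yes: disease only | No |
| Death | No | Only if fatal |
| Malignancy | No | Not applicable |

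Two of the four triggers are therefore unavailable. The SAE exclusion is the narrower one: a serious event attributed to treatment of MPS I, such as a reaction on restarting ERT, would still convene the SMC.

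**How attribution is decided.** Section 10.3 says that "The relationship of the AE to the investigational drug will be determined by the Principal Investigator". It has no rule for judging whether an event off ERT is due to the disease, to the withdrawal or to neither, although that judgement decides whether the SMC meets.

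**Other routes to the SMC, and their timing.** I use 365.25 / 12 / 7 = 4.348 weeks per month.

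1. *Cohort review* (11.5) can take place 4 weeks after the cohort's last infusion. Withdrawal cannot start before Week 12. For the last subject dosed, the review can precede withdrawal by 12 - 4 = 8 weeks. For a subject dosed 4 weeks earlier, the gap is 12 - (4 + 4) = 4 weeks. A cohort's own review can thus come before any withdrawal in those subjects, although a later cohort's review could pick the events up.
2. *Pre-pediatric review* (11.3) needs at least 6 months of data from two adults. That runs past Week 12, so it could include withdrawal events if pediatric dosing is considered.
3. *Rolling review* (SAP section 10 only) is held about every 4-6 months: 4 × 4.348 = 17.4 weeks to 6 × 4.348 = 26.1 weeks. Withdrawal monitoring lasts up to 12 weeks. If a withdrawal starts just after one rolling review, the next falls 17.4 - 12 = 5.4 to 26.1 - 12 = 14.1 weeks after full-length monitoring ends. This is a worst case when no other SMC review intervenes.
4. *Discretionary convening* (12.3) is permitted for excessive or unexpected toxicity, but not required.

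**Length of the window.** Follow-up is 36 × 4.348 = 156.5 weeks. The longest possible time off ERT is 156.5 - 12 = 144.5 weeks, or 144.5 / 156.5 = 92% of follow-up. That needs withdrawal at Week 12 and no resumption. A subject who moves to the long-term follow-up study at Week 52 has at most 52 - 12 = 40 weeks in this study.

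**End of SMC activity.** Under 12.3 and SAP section 10, the SMC stops meeting once no enrolling or dosing decision remains. For the last subject dosed, the whole withdrawal window can fall after that point.

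**The case against.** A reader might infer that deterioration off ERT need never reach the SMC, or that nobody outside the site would know of it. The documents do not support either reading.

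- The cohort, pre-pediatric and SAP rolling reviews carry no disease exclusion, so an active SMC should see these events, though possibly late.
- All SAEs go to the sponsor within 24 hours whatever their cause, and ethics committees are notified under local rules (10.4). Urgent safety matters follow a similar path (10.6).
- Each withdrawal, first or repeat, requires consultation with the sponsor, which will already hold reports of earlier SAEs.
- Monitoring visits are weekly for 4 weeks and then every 2 weeks. Lung function and the 6-minute walk are tested at the withdrawal and follow-up visits, and ERT can be restarted at any time.

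A reader might also infer that the cause of such an event would go unrecorded beyond a relationship to study drug. For SAEs that is wrong: Listing 16.2.7.2 gives reasons for non-relatedness, including attribution to disease.

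These points limit the consequence but do not remove the gap. Sponsor notification is not independent review. The interim monitoring visits may be remote and include no physical examination, lung function or walk test. The rolling review appears in the SAP but not in protocol 12.3, and every SMC route ends when the committee stops meeting.

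One further objection stands and shapes the remedy. Sections 11.5 and 12.3 attach a halt to dosing, pending an approved substantial amendment, to their triggers. Simply deleting the exclusion would bring that consequence with it.

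**Conclusion.** The concern holds in a limited form. A Grade 3+, persistent Grade 2 or serious event attributed to MPS I during ERT withdrawal does not prompt an SMC meeting. While the SMC is active, it would see the event at a scheduled review. The SAP's rolling interval is about 17 to 26 weeks, and protocol 12.3 does not provide for that review. After the SMC stops meeting, it does not see the event at all.

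Two assumptions carry this. First, that disease worsening is the foreseeable harm of withdrawal is an inference from the benefits listed in 1.1; the documents do not state it. Second, the investigator must attribute the event to MPS I, which is natural but which no rule prescribes. The 144 weeks is a ceiling for a subject who stops at Week 12 and never restarts. Withdrawal is optional, and transfer to long-term follow-up shortens the window.

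This is a gap in independent oversight that should be closed. It does not affect the validity of the descriptive analyses.

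**What to change.** Reconcile 11.4 with the exclusions in 11.5, 12.3, the synopsis rows on the SMC and on stopping rules, and SAP section 10.

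1. Add one separate, review-only sentence in those places, for example: *Grade 3 or higher AEs, Grade 2 AEs meeting the existing persistence criterion, and SAEs with onset between the ERT Withdrawal visit and ERT resumption (or end of study) are referred to the SMC for review regardless of attribution to MPS I.*
2. State that this referral does not by itself invoke the dosing halt or the amendment requirement in 11.5 and 12.3. Leave 11.2 and the stopping consequences unchanged.
3. Put the SAP's rolling review into protocol 12.3 so that the two documents agree.
4. State who reviews these events after the SMC stops meeting.
5. Optionally, add an on/off-ERT flag derived from the ERT log to Listings 16.2.7.1 and 16.2.7.2. This is a convenience: AE and ERT dates are already listed by subject, for at most 27 subjects.

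The cost is a few sentences in the protocol, synopsis and SAP. The optional flag uses data already collected. The downside is an occasional extra SMC review of what proves to be natural disease progression. Keeping the existing grade and persistence thresholds limits how often that happens.

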## **13 STATISTICAL ANALYSIS AND DATA ANALYSIS**

The primary objective of this study is to evaluate the safety and tolerability of SB-318. All statistical summaries will be descriptive in nature (e.g., means, standard deviations, and percentages). All subjects who receive any portion of the SB-318 infusion will be included in the analyses, even those who withdraw prematurely from the study. All results will be presented separately for each of the SB-318 dose levels. All analyses, summaries, and listings will be performed using SAS version 9.2 or later.

### **13.1 Determination of Sample Size**

This study will enroll up to 27 subjects (1 subject in Cohort 2 and 2 subjects in each of the other 6 cohorts with potential enrollment of approximately 2 additional subjects in any cohort).

The sample size for this study was not based on statistical considerations, but is considered sufficient to provide preliminary assessments of the safety and tolerability of SB-318 in subjects with MPS I, as well as biochemical changes related to the pathophysiology of MPS I. Subjects who prematurely discontinue the study prior to the 12 months of study follow-up (i.e., subjects who were enrolled but not dosed, were lost to follow-up, or discontinued prematurely for another reason) may be replaced at the discretion of Sangamo.

### **13.2 Statistical Analyses**

Efficacy analyses will be descriptive and exploratory in nature. Continuous variables will be summarized by means, standard deviations, medians, and ranges by cohort. Categorical variables will be summarized with counts and percentages per category by cohort.

### **13.3 Analysis of the Conduct of the Study**

Enrollment, major protocol violations, and discontinuations from the study will be summarized by treatment cohort. The number of subjects who were enrolled, discontinued, and completed the study will be summarized.

Demographic and baseline characteristics, such as age, sex, and race will be summarized using means, standard deviations, medians, and ranges for continuous variables, and proportions for categorical variables. All summaries will be presented overall and by treatment cohort.

### **13.4 Primary Endpoint**

The primary endpoint of this study is the incidence of treatment-emergent AEs (including SAEs). Additional safety evaluations will include:

- Routine hematology, chemistry, and liver function laboratory tests, vital signs, physical exam, ECG, ECHO, and concomitant medications.
- Monitoring of chimerism in post-HSCT subjects.
- Cranial nerve exam and muscle strength testing.
- Serial AFP testing and MRI of liver to evaluate for liver mass.

Safety assessment will be performed on all subjects. All reported AEs will be coded to a standard set of terms using the Medical Dictionary for Regulatory Activities (MedDRA).

Treatment-emergent adverse events will be summarized overall and by treatment cohort. For each subject, the maximum reported severity of each adverse event will be used in the summaries by severity grade. In addition, all serious adverse events and AEs related to study treatment will be summarized.

Laboratory data will be summarized for each time-point at which specimens are collected. Change-from-Baseline values may be calculated for selected laboratory parameters. Shift-tables (Change-from-Baseline relative to the normal range) may be constructed for selected laboratory parameters.

